## 2.3 ACTIVITY OBJECTIVES

The activity objective for this study is to make a preliminary assessment of the activity of RO7297089 on the basis of the following endpoints:

- Objective response rate (ORR), defined as a stringent complete response (sCR), complete response (CR), very good partial response (VGPR), or partial response (PR), as determined by the investigator according to International Myeloma Working Group (IMWG) Uniform Response Criteria ([Appendix 5](#))
- Duration of response (DOR), defined as the time from the first occurrence of a documented objective response to disease progression or death from any cause (whichever occurs first), as determined by the investigator according to IMWG Uniform Response Criteria

## 2.4 IMMUNOGENICITY OBJECTIVES

The immunogenicity objective for this study is to evaluate the immune response to RO7297089 on the basis of the following endpoint:

- Prevalence of anti-drug antibodies (ADAs) at baseline and incidence of ADAs during the study

The exploratory immunogenicity objective for this study is to evaluate potential effects of ADAs on the basis of the following endpoint:

- Relationship between ADA status and safety, PK, biomarker, or activity endpoints

## **2.5 BIOMARKER OBJECTIVE**

The exploratory biomarker objective for this study is to identify and/or evaluate biomarkers that are predictive of response to RO7297089 (i.e., predictive biomarkers), are early surrogates of activity, are associated with progression to a more severe disease state (i.e., prognostic biomarkers), are associated with acquired resistance to RO7297089, are associated with susceptibility to developing adverse events or can lead to improved adverse event monitoring or investigation (i.e., safety biomarkers), can provide evidence of RO7297089 activity (i.e., PD biomarkers), or can increase the knowledge and understanding of disease biology and drug safety, on the basis of the following endpoint:

- Relationship between biomarkers in blood and tissue samples (listed in Section 4.5.7) and safety, PK, activity, immunogenicity, or other biomarker endpoints

## **2.6 ADDITIONAL OBJECTIVE**

An additional objective for this study is to identify a RP2D and regimen for RO7297089 on the basis of the following endpoint:

- Relationship between RO7297089 exposure and safety, PK, activity, and immunogenicity endpoints

## **3. STUDY DESIGN**

### **3.1 DESCRIPTION OF THE STUDY**

This is a first-in-human Phase I, open-label, multicenter, global, dose-escalation study designed to evaluate the safety, tolerability, and pharmacokinetics of RO7297089 and make a preliminary assessment of anti-tumor activity in patients with R/R MM for whom no established therapy for MM is appropriate and available or who are intolerant to those established therapies. The study consists of a screening period of up to 28 days and a minimum follow-up period of 90 days after treatment. Following confirmation of eligibility, patients will receive RO7297089 by IV infusion. Patients will be enrolled in two stages: a dose-escalation stage and an expansion stage. *To mitigate the risk of IRRs, up to three dose-escalation arms that differ in the RO7297089 administration schedule for Cycle 1 may be enrolled in a dose-escalation cohort.* The study will enroll approximately 30–50 patients during the dose-escalation stage and approximately 30 patients during the expansion stage at approximately 12 sites globally. [Figure 1](#) presents an overview of the study design.

[figure not shown]
Patients who do not meet the criteria for participation in this study (screen failure) may qualify for one re-screening opportunity (for a total of two screenings per participant) at the investigator's discretion. Patients must re-sign the consent form prior to re-screening. The investigator will record reasons for screen failure in the screening log (see Section 4.5.1).

All patients will be closely monitored for adverse events throughout the study and for at least 90 days after the final dose of study treatment. Adverse events will be graded according to the NCI CTCAE v5.0, with the exception of CRS, which will be graded according to the Modified Cytokine-Release Syndrome Grading System ([Appendix 9](#)).

Patients may continue treatment with RO7297089 until disease progression as determined by the investigator using IMWG Uniform Response Criteria ([Appendix 5](#)), unacceptable toxicity, start of new anti-cancer therapy, or withdrawal from study participation, whichever occurs first.

A schedule of activities is provided in [Appendix 1](#) and [Appendix 2](#). To characterize the PK properties of RO7297089, blood samples will be taken at various timepoints before and after dosing (see [Appendix 3](#)).

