## **4.4.3            Prohibited Therapy**

Use of the following concomitant therapies is prohibited as described below:

- Investigational therapy (other than protocol-mandated study treatment) for various time periods prior to starting study treatment, depending on the agent (see Section [4.1.2](#)) and during study treatment
- Concomitant therapy intended for the treatment of cancer (including, but not limited to, chemotherapy, immunotherapy, radiotherapy, and herbal therapy) for various time periods prior to starting study treatment, depending on the agent (see Section [4.1.2](#)), and during study treatment, until disease progression is documented and the patient has discontinued study treatment, with the exception of palliative radiotherapy and local therapy under certain circumstances (see Section [4.4.1](#) for details)
- Hormone therapy for the treatment of cancer, whether approved by local regulatory authorities or investigational
  - Adjuvant endocrine therapy for non-metastatic prostate cancer and non-metastatic, hormone-receptor positive breast cancer is permitted.
- Biologic agents other than hematopoietic growth factors, which are allowed if clinically indicated and used in accordance with instructions provided in the package inserts
- Any therapies intended for the treatment of MM, whether approved by local regulatory authorities or investigational

- Live, attenuated vaccines

Patients who require the use of any of these agents will be discontinued from treatment with RO7297089. Patients who are discontinued from study treatment will be followed for safety outcomes for 90 days following the patient's final dose of RO7297089 or until the patient receives another anti-cancer therapy, whichever occurs first.

The above list of medications is not necessarily comprehensive. The investigator should contact the Medical Monitor if questions arise regarding medications not listed above.

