### **4.6 TREATMENT, PATIENT, STUDY, AND SITE DISCONTINUATION**

#### **4.6.1 Study Treatment Discontinuation**

Patients must permanently discontinue study treatment if they experience any of the following:

- Any medical condition that the investigator or Sponsor determines may jeopardize the patient's safety if he or she continues to receive study treatment
- Investigator or Sponsor determination that treatment discontinuation is in the best interest of the patient
- Pregnancy
- Use of an anticancer therapy not required per protocol
- Symptomatic deterioration attributed to disease progression
- Confirmed disease progression per investigator assessment according to IMWG Uniform Response Criteria ([Appendix 5](#))
- Patient decision

The primary reason for study treatment discontinuation should be documented on the appropriate eCRF. Patients who discontinue study treatment prematurely will not be replaced unless enrolled in the dose-escalation cohorts and discontinue prior to completion of the 14-day DLT assessment window.

Patients will return to the clinic for a treatment discontinuation visit 30 ( $\pm$  10) days after the final dose of study drug (see [Appendix 1](#) for additional details). Additionally, patients who discontinue study treatment for reasons other than documented disease progression or relapse should continue to be followed as described in [Appendix 2](#) until disease progression, start of new anti-cancer therapy, or withdrawal from study participation, whichever occurs first.

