### **5.3.1 Adverse Event Reporting Period**

Investigators will seek information on adverse events at each patient contact. All adverse events, whether reported by the patient or noted by study personnel, will be recorded in the patient's medical record and on the Adverse Event eCRF.

After informed consent has been obtained but prior to initiation of study drug, only serious adverse events caused by a protocol-mandated intervention (e.g., invasive procedures such as biopsies, discontinuation of medications) should be reported (see Section 5.4.2 for instructions for reporting serious adverse events).

After initiation of study drug, all adverse events will be reported until 90 days after the final dose of study drug or until initiation of new systemic anti-cancer therapy, whichever occurs first.

Instructions for reporting adverse events that occur after the adverse event reporting period are provided in Section 5.6.

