## Appendix 2 Schedule of Activities: Post-Treatment Follow-Up

Assessments/Procedures	Post-Treatment Follow-Up a
Targeted physical examination b	Every 3 months
Vital signs (blood pressure, pulse rate, and body temperature)	Every 3 months
ECOG Performance Status	Every 3 months
Tumor assessments including SPEP with SIFE and SFLCs performed centrally; UPEP with UIFE and imaging performed locally as clinically indicated	Every 3 months
Total IgA, IgG, IgM	Every 3 months
Hematology c	Every 3 months × 2, then every 6 months
Serum chemistry d	Every 3 months × 2, then every 6 months
Bone marrow biopsy and aspirate e	As needed to confirm relapse

ADA = anti-drug antibody; ECOG = Eastern Cooperative Oncology Group; eCRF = electronic Case Report Form; PK = pharmacokinetic; SFLC = serum free light chain; SIFE = serum immunofixation electrophoresis; SPEP = serum protein electrophoresis; UIFE = urine immunofixation electrophoresis; UPEP = urine protein electrophoresis.

- a Schedule corresponds to visit timepoints only for patients who do not discontinue the study due to progressive disease. Perform assessments until disease progression, start of new anti-cancer therapy, or withdrawal from study participation, whichever occurs first. Continue to follow patients on this schedule timed from the treatment termination visit 30 days ( $\pm 10$  days) after the last dose of RO7297089 administered. The first 2 visits should occur within  $\pm 7$  days from the scheduled date, while subsequent visits should occur within  $\pm 14$  days from the scheduled date.
- b Targeted physical examinations should be limited to systems of primary relevance (i.e., cardiovascular, respiratory, neurologic, and any system that might be associated with tumor assessment [e.g., those systems associated with symptoms], or potential drug-related toxicity; see Section 5.1.1). Changes from baseline abnormalities should be recorded in patient notes. New or worsened clinically significant abnormalities should be recorded as adverse events on the Adverse Event eCRF.
- c Hematology includes WBC count, RBC count, hemoglobin, hematocrit, platelet count, and differential count (neutrophils, eosinophils, basophils, monocytes, lymphocytes, other cells [if present]).

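### Adverse events are to be monitored for 90 days after the last dose, but no contact is required between the Day 30 visit and Day 90, and patients who stop for progression have none required after Day 30

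*Combined protocol and SAP*

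**What the plan says.** **The commitment.** Section 3.1 and the synopsis promise that all patients will be "closely monitored for adverse events throughout the study and for at least 90 days after the final dose of study treatment". Section 4.4.3 says that patients taken off treatment are "followed for safety outcomes for 90 days following the patient's final dose of RO7297089", or until another anti-cancer therapy if that comes first. Section 5.3.1 sets the reporting rule: "all adverse events will be reported until 90 days after the final dose of study drug or until initiation of new systemic anti-cancer therapy", whichever is earlier. Section 5.4.2.2 gives 90 days for serious adverse events and adverse events of special interest, without the new-therapy exception.

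**How events are found.** Section 5.3.1: "Investigators will seek information on adverse events at each patient contact".

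**The contacts.**
- Section 4.6.1: "Patients will return to the clinic for a treatment discontinuation visit 30" (±10) days after the final dose. Appendix 1 (footnote v) has the same timing and marks adverse events at that visit.
- Appendix 2, footnote a: "Schedule corresponds to visit timepoints only for patients who do not discontinue the study due to progressive disease". The visits are every 3 months, and the anchor is explicit: "Continue to follow patients on this schedule timed from the treatment termination visit 30 days" (±10) after the last dose. The first two visits have a window of ±7 days. The table has no adverse event row.
- Section 4.6.1.1: survival and subsequent-therapy information may be collected about every 3 months by telephone, from medical records or at visits. Adverse events are not mentioned.

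**The concern.** The protocol finds adverse events by asking at contacts, so a 90-day period is only as good as the contacts inside it. If the last required contact is at about one third of the period, a record with no event between Day 30 and Day 90 cannot be told apart from a record where nobody asked.

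The incidence and severity of adverse events is a primary safety endpoint of this first-in-human study (Section 2.1). Some of the named risks can appear late: Section 5.1.1.3 describes hypogammaglobulinemia with an increased risk of infection, and Section 5.2.3 makes Grade 3 or higher infection an event of special interest. For patients who progressed, the start date of new therapy, which closes the all-event reporting period, is also collected after Day 30 only through the optional follow-up. The end of each such patient's observation period may then be unknown as well.

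**Working it through.** No sample-size or error-rate figure is involved. The check is calendar arithmetic, then a search for anything that fills the gap.

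**Inputs**
- Adverse event period: 90 days after the final dose (Sections 3.1 and 5.3.1).
- Last visit common to all: Day 30 ± 10, so Day 20 to 40 (Section 4.6.1, Appendix 1).
- First Appendix 2 visit: 3 months after that visit, ±7 days.
- Assumption: the documents do not give 3 months in days. I use 90 to 92, with 84 (12 weeks) as the shortest plausible reading.

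**Step 1. Days without a required contact** = 90 − day of the last common visit.
- Nominal: 90 − 30 = 60 days (60/90 = 0.67).
- Range: 90 − 40 = 50 days (0.56) to 90 − 20 = 70 days (0.78).

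**Step 2. First Appendix 2 visit** = day of the last common visit + 3 months ± 7.
- Nominal: 30 + 90 = 120 to 30 + 92 = 122, so about Day 121.
- Earliest: 20 + 90 − 7 = 103. Latest: 40 + 92 + 7 = 139.
- With 84 days: 20 + 84 − 7 = 97 at the earliest.

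Every version falls after Day 90. Counted from the last dose instead, the first visit would fall between 90 − 7 = 83 and 92 + 7 = 99, but footnote a states the other anchor.

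**Step 3. Does anything else fill the gap?**

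| Provision | Required contact between the Day 30 visit and Day 90? |
|---|---|
| Appendix 2 visits | No. First at about Day 121; patients who stop for progression excluded |
| Section 4.6.1.1 survival follow-up | No. Optional, about 3-monthly, records alone suffice |
| Section 5.1.2.1 pointer to Appendix 3 | No. A sampling schedule that ends at the end-of-treatment visit |
| Section 5.5.1 follow-up to resolution | Only for events already identified |
| Sections 5.3.5.8 and 5.4.2.2 (deaths, serious events, special interest) | No. A duty to report once the event is known, not a contact |

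**Step 4. By type of patient**
- Stopped for progression: asked about adverse events at Day 30 (±10), with no required contact afterwards.
- Stopped for another reason and still in Appendix 2 follow-up: asked at Day 30 (±10), then at about Day 121.

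**The case against.** The strongest reply has four parts.

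1. *The period is often shorter than 90 days.* Reporting of all adverse events ends when new systemic therapy starts, and patients who have progressed are the likeliest to move on. This stands: the 60 days is a maximum for such patients. The documents do not say how many there will be, and eligibility requires that no established therapy is appropriate and available, or intolerance to it, so quick switching cannot be assumed. Section 5.4.2.2 keeps the full 90 days for serious events and events of special interest.

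2. *Patients in Appendix 2 are still asked.* Section 5.3.1 applies at the Day 121 visit, Section 4.5.2 calls for an interval history at each follow-up examination, and the model questions in Section 5.3.2 cover the time since the previous visit. Footnote b of Appendix 2 sends new abnormalities to the adverse event form. This stands too. A reader might infer that everything after Day 30 rests on spontaneous reports. For these patients it does not; their weakness is delayed recall.

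3. *Serious events will surface anyway.* Deaths, serious events and events of special interest are reportable within 24 hours of the investigator learning of them. This makes their loss less likely but does not exclude it, because the duty starts only when the investigator hears of the event.

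4. *A survival call is itself a patient contact*, so adverse events would be asked about. That is true if a call is made, but the call is optional, may be replaced by a records check, and at about 3 months falls near or after the end of the period.

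**Conclusion.** The point holds. Followed as written, the schedule leaves 60 days of the 90-day period (50 to 70 with the visit window) without a required contact, less where new systemic therapy starts earlier. The clearest gap is in patients who stop for progression and have not begun new therapy. The timing rests on the anchor stated in Appendix 2 and on 3 months being 84 to 92 days; no value in that range brings the first visit inside Day 90.

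Three stronger readings are not supported:
- *Patients who progress get no adverse event follow-up after treatment.* They have the Day 30 visit, at which Appendix 1 collects adverse events.
- *Late events are under-counted.* That is a risk, mainly for non-serious events. The documents do not allow its size to be estimated.
- *The dose finding is compromised.* DLTs are assessed in a 14-day window (extendable by 7 days) around the first target doses, so DLT and MTD assessment does not draw on Days 30 to 90 after the last dose.

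What remains is a mismatch between the stated monitoring period and the schedule for a primary safety endpoint. It should be corrected because the correction is cheap.

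**What to change.** Add to Appendix 2 a safety contact at about Day 90 after the final dose, telephone acceptable, for all treated patients, and amend footnote a so that it includes those who stop for progression. Placing it on or just after Day 90 lets the question cover the whole period. It should collect adverse events, serious events and events of special interest since the Day 30 visit, and the start date of any new anti-cancer therapy. Give Appendix 2 an adverse event row, and refer to the contact in Sections 4.6.1 and 5.3.1. Where possible, combine it with the first survival call under Section 4.6.1.1.

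The cost is one call per patient, so at most about 60 to 80 calls at the planned enrollment in Section 4.1, and one schedule row. No clinic procedure is added and treatment is unchanged. If the sponsor prefers not to add the contact, Section 5.3.1 should say plainly that for patients who stop for progression, events after the Day 30 visit are collected only if they come to the investigator's attention, and the safety report should carry that limitation.

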**Figure 1 Study Design**

**Notes:**

RO7297089 is administered by IV infusion, with a cycle length of 14 days. The Cycle 1 administration schedule is dependent on the assigned treatment arm (see Figure 2). From Cycle 2 onwards, RO7297089 is administered on Days 1 and 8 of each cycle.

Cohort must clear the DLT assessment window to open next cohort. The DLT assessment window is 14 days (see Figure 2).

Backfill cohorts are ungated based on evidence of clinical activity (e.g., decrease in M-protein) and/or PD activity (e.g., NK cell activation). Dose-escalation decisions are based on totality of data (clinical, safety, PK, biomarker). Dose recommended will not exceed dose recommended by the mCRM-EWOC model.

DLT=dose-limiting toxicity; mCRM-EWOC=modified continual reassessment method of escalation with overdose control; MTD=maximum tolerated dose; NK=natural killer; RP2D=recommended Phase II dose; PD=pharmacodynamic; PK=pharmacokinetic; TBD=to be determined.

*For all arms, the target dose refers to the highest dose administered in Cycle 1; this target dose will be administered on Day 1 and Day 8 of subsequent cycles.*

[figure not shown]
*Enrollment in the dose-escalation arms will be managed as follows:*

- *For new dose cohorts, all patients will enroll in Arm A unless criteria have been met for opening Arms B or C in a previous cohort.*
- *Arm B may open if the planned infusion time for Arm A exceeds 4 hours on Cycle 1, Day 1. Arm C may open if 2 or more patients in Arm B of that dose cohort experience any grade IRR that precludes the patient from receiving the full target dose during Cycle 1, Day 1 and Day 2.*

[figure not shown]
- Once Arm B is open, Arm A for that dose cohort may close to further enrollment and may not open for subsequent dose cohorts. Similarly, once Arm C is open, Arm B for that dose cohort may close to further enrollment and may not open for subsequent dose cohorts.
- A minimum of 3 patients must complete the DLT assessment period for a given arm (Arm A, B, or C) before dose escalation for that arm may occur.

**Figure 2 Dose-Escalation Arms: Study Drug Administration for Cycle 1**

[figure not shown]
**Arm A (Flat Dose)**

**Arm B (Split Dose)a**

**Arm C (Step Dose)c**

D = day; DLT = dose-limiting toxicity; IRR = infusion-related reaction.

Notes: One treatment cycle is 14 days. Target dose is the highest dose administered in Cycle 1. DLT window is 14 days.

a Arm B may open if the planned infusion time exceeds 4 hours on Cycle 1, Day 1.

b If the Day 1 dose is associated with Grade  $\geq 2$  IRR, the ratio may be adjusted so that a smaller percentage of the dose is administered on Day 1, with the remainder of the dose administered on Day 2.

c Arm C may open if more than one patient in Arm B of that dose cohort experiences an IRR that precludes the patient from receiving the full target dose during Cycle 1, Day 1 and Day 2.

Dose escalations will be guided by the modified continual reassessment method of escalation with overdose control (mCRM-EWOC) model (Neuenschwander et al. 2008; [Appendix 11](#)). All cohorts will enroll a minimum of 3 patients. Enrollment of the first 2 patients in each arm of each dose-escalation cohort will be staggered such that the respective Cycle 1, Day 1 treatments are administered  $\geq 72$  hours apart. The maximal

dose escalation increment recommended by the model will be 3-fold. In addition, the relevant demographic, adverse event, laboratory, dose administration, and available PK data will be reviewed prior to dose-escalation decisions, which will be made by an Internal Safety Committee (ISC) in consultation with the investigator (see Section 3.1.5 for more information about the ISC).

Evidence of clinical activity at a given dose level (e.g., decrease in serum monoclonal protein [M-protein]) or PD activity (e.g., NK cell activation) may ungate backfill cohorts at doses that have already completed DLT assessment and have been found not to exceed the MTD in escalation cohorts. DLT information from patients in these back-fill cohorts will be used to inform the mCRM-EWOC model.

Patients will be closely monitored for adverse events during a DLT assessment window (14 days), *as defined above for each arm*. Adverse events identified as DLTs, as defined below (see Section 3.1.1.1), will be reported to the Sponsor within 24 hours.

Patients who discontinue from the study prior to completing the DLT assessment window for reasons other than a DLT will be considered non-evaluable for dose-escalation decisions and MTD assessments and will be replaced by an additional patient at that same dose level. Patients must receive two *planned target* doses of RO7297089 during the DLT assessment window to be considered DLT-evaluable. Treatment delays during the first cycle of RO7297089 will be allowed if they are less than one cycle (i.e., <14 days); under these circumstances, the DLT assessment window may be extended up to *an additional 7 days* in order to capture two *planned target* doses of treatment. Patients who receive supportive care during the DLT assessment window that confounds the evaluation of DLTs (not including supportive care described below as part of the DLT definition) may be replaced at the discretion of the Medical Monitor.

As described in Section 3.1.5, the ISC will additionally review cumulative safety data and make recommendations regarding overall study conduct to ensure patient safety while receiving study treatment. These recommendations include suspending patient enrollment based on the overall benefit-risk profile of RO7297089 during dose escalation.

